STUDY POPULATION	
Infants born between 22+0 and 31+6 weeks' gestation admitted to a participating centre from whom prospective parental informed consent can be obtained will be considered eligible. If parental consent cannot be obtained or if lung imaging or blood sampling would compromise clinical care or well-being, the infant will be considered ineligible for participation in this study.
 
A sample size of 550 infants will allow for prediction models of BPD using up to 12 variables from the respiratory phenotype data collected in the first 7 days after birth with a C-index of 0.75 (assuming 5% lost to follow up). This sample size will have sufficient power to address the endotyping and respiratory health

	objectives of the study at 1- and 2-years corrected age, with account for anticipated loss to follow up rates.
DESCRIPTION OF SITES ENROLLING PARTICIPANTS	All Level 6 NICUs in Melbourne, Victoria (Australia) will be invited to participate (5 sites maximum).
RECRUITMENT PERIOD	Approximately 5 years after first infant enrolled.
FOLLOW-UP PERIOD	2 years, assessments at 1- and 2-years (corrected).
PARTICIPANT DURATION	2 years, corrected age from birth.

GLOSSARY OF ABBREVIATIONS

ABBREVIATION	TERM
AE	Adverse Event
ANOVA	Analysis of Variance
ANZNN	Australian and New Zealand Neonatal Network: a collaborative network which monitors and reports on the care of high-risk newborns in all Australian and New Zealand neonatal intensive care units.
BPD	Bronchopulmonary dysplasia: a form of chronic lung disease that affects preterm infants
CLD	Chronic Lung Disease
CCe	Coordinating Centre
CRF / eCRF	Case Report Form / electronic Case Report Form
CXR	Chest Radiography
DCCe	Data Coordinating Centre
DMS	Data Management System
DSMC	Data Safety Monitoring Committee
EDTA	Ethylenediaminetetraacetic acid: used as an anticoagulant in blood tubes
EIT	Electrical Impedance Tomography
EMR	Electronic Medical Record
ETT	Endotracheal Tube
FiO₂	Fraction of Inspired Oxygen
GA	Gestational age
GCP	Good Clinical Practice
HR	Heart Rate
HREC	Human Research Ethics Committee
IVH	Intraventricular Haemorrhage
LCA	Latent Class Analysis
LUS	Lung Ultrasound
LUSS	Lung Ultrasound Score

Study Name: The BLUEPRINT Study

Protocol Number: 107608

Version & date: Version 1.2, dated 9 July 2024

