11 STATISTICAL METHODS

11.1 Sample Size Estimation

The sample size for BLUEPRINT is designed to address the robustness of early respiratory phenotypes identified predicting BPD. The prevalence of survival with BPD within the ANZNN is 0.69. Based on the R package *pmsampsize* version 1.1.3 described by Riley et al in “*Calculating the sample size required for developing a clinical prediction model*”,⁽³⁶⁾ we estimated that the following sample size will be required to develop a clinical risk prediction model with BPD (yes/no) as the outcome: assuming a BPD prevalence of 0.69 (69%; all grades) and a moderate C-index of 0.75 is achievable (latest estimates from PRELIM manuscript support this) with a binary logistic regression prediction model with BPD (yes/no) as the outcome, a minimum sample size of 500, 550 and 600 infants was estimated based on 10, 11 or 12 predictor variables respectively (from any domain of clinical, imaging and protein data). We estimate that the predictive model developed in BLUEPRINT may have up to 10-12 predictor variables which is partly based on the latest PRELIM manuscript where several basic clinical covariates (e.g. gender, gestational age) and only single proteins were included (given the limited sample size in PRELIM), however there were multiple proteins that were significantly correlated with BPD and there will be additional clinical covariates and other model terms (interactions, non-linear terms, which are counted as additional predictor variables terms in the *pmsampsize* sample size estimation) that will likely be critical to include in the BLUEPRINT study in order to achieve high performing predictive models.

The calculation above derived from the *pmsampsize* R package considers multiple criteria to arrive at an appropriate sample size that ensures precise predictions, minimises prediction errors and model overfitting/optimism, and allows for sufficient stratification by factors known to exert a strong signal on neonatal outcomes (e.g. gestational age/weight, sex and intubation in first 10 days).

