This sample size prediction assumes the distribution of births within the 22-25+6-, 26-28+6- and 29-31+6-week GA cohorts as reported in the ANZNN. Between 2018-2020, approximately 750 infants aged 22-32 weeks' gestation were born per annum in Victoria who would have met the projects eligibility criteria; 37% <28 weeks' GA, overall mortality 7% (Data Safer Care Victoria). To achieve the desired sample size a recruitment rate of 20-25% of all eligible births (approximately 2250 births) would be required. Assuming a 5% loss to follow up/withdrawal rate between the first week after birth and BPD assessment a sample size of 550 infants included into the primary aim of the study (early life respiratory phenotype description) would allow 525 infants for inclusion in the BPD prediction modelling data set. This should also allow for approximately 400-450 surviving infants available for 2-year follow up (assuming >80% retainment rate after discharge).

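### The synopsis promises a BPD model with up to 12 variables from 550 infants, but Section 11.1's own figures support 10 predictor terms after the stated 5% loss

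*Protocol*

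**What the plan says.** The Protocol synopsis, under Study population, says "A sample size of 550 infants will allow for prediction models of BPD using up to 12 variables", and qualifies this as "with a C-index of 0.75 (assuming 5% lost to follow up".

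Section 11.1 (Sample Size Estimation) gives the calculation behind it:

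- **Method:** "Based on the R package *pmsampsize* version 1.1.3", for a binary logistic model with BPD yes/no as the outcome.
- **Inputs:** "assuming a BPD prevalence of 0.69 (69%; all grades) and a moderate C-index of 0.75 is achievable".
- **Result:** "a minimum sample size of 500, 550 and 600 infants was estimated based on 10, 11 or 12 predictor variables respectively".
- **What counts as a predictor:** interactions and non-linear terms, "which are counted as additional predictor variables terms in the *pmsampsize* sample size estimation".
- **After loss:** with 5% lost between the first week and the BPD assessment, 550 infants "would allow 525 infants for inclusion in the BPD prediction modelling data set".

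Section 11.1 also expects the model to need up to 10 to 12 predictor variables. Planned enrolment is 550 in the synopsis and in Sections 1.3 and 4.2.

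**The concern.** The synopsis and Section 11.1 describe the same model, outcome, C-index, enrolment and loss rate, yet give different answers on how many predictors the sample can carry. The synopsis says 12. Section 11.1 puts the requirement for 12 at 600, which is above both the enrolment target and the modelling set.

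This is the only sample-size calculation in the protocol, and Section 11.1 says that the study was sized for BPD prediction. A team relying on the synopsis would plan a model larger than the calculation allows.

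The wording could widen the gap. The synopsis speaks of variables, while Section 11.1 counts every interaction and non-linear term and expects such terms to be important. Someone who chose 12 measured variables and then added terms would go past 12 parameters.

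**Working it through.** **1. The protocol's own figures side by side**

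| Predictor terms | Infants required (11.1) | Met by 525, as printed? | Met by 550 x 0.95 = 522.5? | Met by 550 with no loss? |
|---|---|---|---|---|
| 10 | 500 | yes | yes | yes |
| 11 | 550 | no | no | yes |
| 12 | 600 | no | no | no |

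No column reaches 12. The printed 525 implies a loss of 25/550 = 4.5%. At 5% the figure is 522.5. The difference does not change the conclusion, since both lie between 500 and 550.

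**2. Reproducing 500, 550 and 600**

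Inputs from Section 11.1: prevalence 0.69, C-index 0.75. Assumptions not stated in the protocol: the package defaults of shrinkage S = 0.90, optimism in Nagelkerke R² of at most 0.05, and overall risk estimated to within 0.05.

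The Cox-Snell R² implied by these inputs came from 1,000,000 simulated records with a normal linear predictor. Non-events have mean 0 and events have mean √2 x z(0.75) = √2 x 0.6745 = 0.954, both with SD 1. This gave R² = 0.1626.

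- *Shrinkage criterion:* n = P / [(S − 1) x ln(1 − R²/S)]. Here ln(1 − 0.1626/0.90) = −0.1993, so each term needs 1/(0.1 x 0.1993) = about 50.2 infants. For P = 10, 11 and 12, n = 502, 553 and 603.
- *Optimism criterion:* 253, 279 and 304.
- *Overall-risk criterion:* (1.96/0.05)² x 0.69 x 0.31 = 329.

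The shrinkage criterion drives the result in each case. The values 502, 553 and 603 reproduce the stated 500, 550 and 600 to within 1%. The stated figures therefore contain no allowance for loss. They are the sizes of the data set in which the model is developed.

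**3. What the modelling set supports**

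Largest P at S = 0.90:

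- n = 522: 10.4
- n = 525: 10.5
- n = 550: 10.96 (11 by the protocol's rounded figures)

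Expected shrinkage, solving the same formula for S:

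| n | 10 terms | 11 terms | 12 terms |
|---|---|---|---|
| 522 | 0.9034 | 0.8949 | 0.8865 |
| 525 | 0.9039 | 0.8954 | 0.8871 |
| 550 | 0.9078 | 0.8996 | 0.8916 |

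**4. Enrolment needed at 5% loss**

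- 10 terms: 500/0.95 = 527
- 11 terms: 550/0.95 = 579
- 12 terms: 600/0.95 = 632

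**5. Sensitivity to the C-index**

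| C-index | n for 10 terms | n for 11 terms | n for 12 terms |
|---|---|---|---|
| 0.74 | 548 | 603 | 658 |
| 0.75 | 502 | 553 | 603 |
| 0.76 | 462 | 508 | 554 |

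At 0.76, about 522 infants would carry 11 terms but still not 12. At 0.74 they would not carry 10.

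**The case against.** The strongest reply is that little turns on the difference. Section 11.1 gives the correct requirement for each number of predictors, so a careful reader is not misled. BPD prediction is a secondary objective of an observational cohort. The expected model size is given as a range whose lower end the design supports, and Section 11.2 sets a minimum of only 7 inputs. Section 11.2 also plans cross-validation and bootstrapping to adjust for optimism, so a 12-term model would not be taken at face value. Finally, the protocol names no shrinkage target, so a miss against 0.90 is a miss against an assumed default.

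Most of this stands, and it limits the seriousness of the point. It does not remove the contradiction, which is visible in the protocol's own 500, 550, 600 and 525 without any assumption about shrinkage. Internal validation can measure and correct optimism, but it does not make 550 infants meet a stated requirement of 600.

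Three stronger readings are tempting, and the documents do not support them:

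- *Deaths shrink the modelling set further.* The 7% mortality in Section 11.1 describes eligible Victorian births in 2018-2020. It is not a loss rate after enrolment. Section 6.2.7 keeps some respiratory deaths in the model as severe BPD. The share of deaths that would be lost is not given.
- *The 400-450 children expected at 2 years is wrong.* Section 11.1 assumes retention above 80%, and exactly 80% of 522 is 418, inside that range.
- *The claim beginning "This sample size will have sufficient power to address the endotyping and respiratory health" is shown to be false.* No calculation for it appears in the protocol, but Section 11.2 defers analysis detail to a separate SAP that is not at hand. Nothing in the figures above tests the claim.

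**Conclusion.** The synopsis is wrong as written. With 550 enrolled and 5% loss, Section 11.1's figures support 10 predictor terms, not 12. The gap for 12 terms is 600 − 522 = 78 infants in the modelling set, or 632 − 550 = 82 in enrolment.

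That 12 is out of reach rests only on the protocol's own numbers, and it also holds at a C-index of 0.76. The exact figure of 10 depends on the stated C-index of 0.75 and prevalence of 0.69. The shrinkage values of about 0.886 for 12 terms and 0.903 for 10 depend in addition on the assumed package defaults.

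A reader might infer that a 12-term model would be seriously overfitted or invalid. The size of the shortfall does not support that: expected shrinkage falls below the default target by about 0.014. This is a should-fix point, because it corrects a headline figure for the study's only stated sample-size basis.

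**What to change.** 1. In the synopsis, replace the 12 variables with up to 10 predictor parameters, counting interaction and non-linear terms, so that the unit matches Section 11.1.
2. In Section 11.1, cap the expected range of 10 to 12 at 10 for 550 enrolled.
3. In Section 11.1, correct 525 to about 522 (550 x 0.95 = 522.5).

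If the investigators want to keep 12 terms, the alternative is to plan about 632 enrolled (600/0.95) and revise the enrolment target wherever it appears.

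The first route changes wording only, with no extra infants and no change to conduct. Its downside is a slightly less favourable stated model size. The second route means about 82 more infants.

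### The synopsis promises a 12-variable BPD model from 550 infants, but Section 11.1 requires 600 for 12 terms and leaves 525 for the model, which supports 10

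*Protocol*

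**What the plan says.** The synopsis, under Study population, says "A sample size of 550 infants will allow for prediction models of BPD using up to 12 variables" measured in the first 7 days, "with a C-index of 0.75 (assuming 5% lost to follow up").

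Section 11.1 (Sample Size Estimation) gives the calculation behind this. It names the R package *pmsampsize* and works from "assuming a BPD prevalence of 0.69 (69%; all grades) and a moderate C-index of 0.75 is achievable". From these inputs "a minimum sample size of 500, 550 and 600 infants was estimated based on 10, 11 or 12 predictor variables respectively". It then says "We estimate that the predictive model developed in BLUEPRINT may have up to 10-12 predictor variables", and explains that interactions and non-linear terms are included in that count: "which are counted as additional predictor variables terms in the *pmsampsize* sample size estimation".

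The same section goes on to attrition: "Assuming a 5% loss to follow up/withdrawal rate between the first week after birth and BPD assessment", the 550 infants in the primary aim "would allow 525 infants for inclusion in the BPD prediction modelling data set".

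**The concern.** The two parts of the protocol give different predictor budgets for the same model, outcome and C-index. The synopsis pairs 550 infants with 12 variables, whereas Section 11.1 pairs 550 with 11 terms and 600 with 12, and expects only 525 infants in the model. The expected range of 10 to 12 predictors in Section 11.1 has the same problem when set beside the 525.

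This is the only calculation in the protocol that sizes the study, and the modelling team will work to the predictor budget it gives. The synopsis also speaks of variables, while Section 11.1 counts model terms. A model with 12 variables and a few interactions or splines would use more than 12 terms, so a reader who relies on the synopsis could overspend the budget by more than the plain 10-versus-12 gap.

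**Working it through.** **Step 1: the printed figures alone.**

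| Predictor terms | Minimum size, Section 11.1 | Expected in BPD model, Section 11.1 | Margin |
|---|---|---|---|
| 10 | 500 | 525 | +25 |
| 11 | 550 | 525 | −25 |
| 12 | 600 | 525 | −75 |

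Attrition: 550 × 0.95 = 522.5. The protocol prints 525, and the difference does not affect the result.

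If the minima are read as numbers enrolled rather than analysed, 550 still reaches only 11 terms. No reading gives 12.

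Enrolment needed at 5% loss: for 12 terms 600 / 0.95 = 631.6, so 632; for 11 terms 550 / 0.95 = 578.9, so 579.

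**Step 2: reproducing the minima.** Inputs from Section 11.1 are prevalence 0.69 and C-index 0.75. Assumed, because the protocol does not state them, are the package's usual settings: shrinkage target S = 0.90, optimism in Nagelkerke R² of at most 0.05, and overall risk estimated to within ±0.05.

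The C-index is converted to a Cox-Snell R² with a linear predictor that is normal within each outcome group. By numerical integration this gives R² = 0.1624.

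Shrinkage criterion: n = P / [(S − 1) × ln(1 − R²/S)].

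- R²/S = 0.1624 / 0.90 = 0.1804, and ln(1 − 0.1804) = −0.1990.
- (S − 1) × ln(1 − R²/S) = (−0.10) × (−0.1990) = 0.01990.
- P = 10: 10 / 0.01990 gives 503. P = 11 gives 553. P = 12 gives 603.

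The optimism criterion needs 253, 279 and 304 infants. The overall-risk criterion needs (1.96 / 0.05)² × 0.69 × 0.31 = 329. Neither is the limiting one. The printed 500, 550 and 600 are therefore reproduced to within 1%.

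**Step 3: what 525 supports.** Inverting the shrinkage criterion, P = 525 × 0.01990 = 10.4 terms, so 10 whole terms. Solving the same equation for S at n = 525:

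| Terms | Expected shrinkage at 525 | Meets 0.90? |
|---|---|---|
| 10 | 0.904 | yes |
| 11 | 0.895 | no |
| 12 | 0.887 | no |

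**Step 4: sensitivity to the C-index.** At C = 0.74 the budget at 525 is 9.6 terms, and at C = 0.76 it is 11.4. Twelve is not reached at any of these values.

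**The case against.** Several points on the other side are sound and limit the finding.

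- **The practical shortfall is small.** Twelve terms at 525 miss a 0.90 shrinkage target by about 0.013. A reader might infer that a 12-term model would be badly overfitted. The figures do not support that, and Section 11.2 already commits to cross-validation and bootstrapping to correct for optimism.
- **The 0.90 target is not in the protocol.** It is an assumption about the package settings, so the shrinkage figures depend on it. The comparison of 525 with 550 and 600 does not.
- **The minima are not labelled as analysed numbers.** Reading them that way is natural for model development and fits the later statement about 525, but the limit of 10, rather than 11, rests on that reading. That 12 is paired with 600 needs no interpretation.
- **The predictor count is tentative.** Section 11.1 gives 10 to 12 as an upper range and Section 11.2 sets only a floor of 7 inputs, so a model of 7 to 10 terms complies and fits the sample. BPD prediction is also a secondary objective (Section 3.1.2).

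Two further inferences should not be drawn. One is that the printed minima are wrong or materially rounded down. They lie within 1% of the recomputed values, and small changes in the third decimal of R² move the result by a few infants. The other is that the synopsis promises a C-index of 0.75 as a result. Section 11.1 plainly treats it as an assumption, and the synopsis merely abbreviates it.

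None of this reconciles 12 variables with 550 infants.

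**Conclusion.** The contradiction stands on the protocol's own figures. The synopsis states up to 12 variables. Section 11.1 supports 10 terms at the 525 infants expected in the model, and at most 11 if there were no loss. Twelve would need 600 analysed.

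The gap is 75 infants, or two model terms. Its statistical consequence is modest: expected shrinkage of about 0.887 against an assumed target of 0.90. The error lies in the stated predictor budget, since the sample size calculation itself reproduces.

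This should be fixed because it misstates the one quantity that the sample size was set to guarantee. It does not undermine the study, and it does not call the enrolment target of 550 into question for the primary objective.

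**What to change.** In the synopsis, replace the 12-variable claim with wording such as: *up to 10 predictor parameters, counting interaction and non-linear terms, at 525 infants analysed, assuming a C-index of 0.75*. In Section 11.1, change the expected range of 10 to 12 predictors to match.

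Leave the printed minima of 500, 550 and 600 as they are, or have the sponsor print the exact output of its own package run. It would help to state the shrinkage target used and that the minima refer to infants analysed.

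If the sponsor wants to keep 12 terms, the alternative is to plan for about 632 enrolled.

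The first option costs only wording in two places and a slightly smaller predictor budget. Enrolment, procedures and data collection do not change.

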3.2 Outcomes

Table 3a defines the outcomes measures in relation to objectives and confounders.

Table 3a Listing objectives, exposure, outcomes and outcome measures, and confounders

PRIMARY OBJECTIVE
To comprehensively define the respiratory phenotype in the first 7 days after birth of preterm infants born between 22+0 and 31+6 weeks' gestation.

Exposure:
 
Day 7 after birth.

Outcome & outcome measure:
 
Functional endotypes defined from clinical, plasma protein and lung imaging measures using latent class analysis followed by external validation via group-based trajectory modelling.

Confounding factors:
 
Maternal and antenatal factors and management, clinical decisions regarding respiratory support (site and clinician differences in guidelines and management), preterm non-respiratory complications (such as infection, neurological disease, necrotising enterocolitis).

SECONDARY OBJECTIVES
To compare the respiratory endotypes associated with different respiratory outcomes using observational data at 72 hours after birth in preterm infants born between 22+0 and 31+6 weeks' gestation.

Outcome & outcome measure
 
Functional endotypes defined from clinical, plasma protein and lung imaging measures using latent class analysis (LCA) followed by external validation via group-based trajectory modelling.

To develop the first functional classification of preterm respiratory disease using a combination of clinical, lung imaging and molecular biomarkers.

Outcome & outcome measure
 
Temporally specific respiratory phenotypes derived from longitudinal latent class analysis of clinical, lung imaging and molecular biomarker data from all time points of the study.

To determine how specific early preterm phenotypes relate to a diagnosis of BPD and use this delineation to develop a predictive modelling tool for the early diagnosis of BPD.

Outcome & outcome measure

BPD status at 36 weeks' corrected PMA using Walsh Definition and Jensen Grade of Severity and functional endotypes determined above.
SECONDARY OBJECTIVES cont.
To determine how specific early preterm endotypes relate to outcomes of the primary NICU admission, including duration of invasive mechanical ventilation and supplementary oxygen support, mortality, need for supplementary oxygen at discharge home.
Outcome & outcome measure

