Development of a biomarker-based BPD risk (and 1 and 2 year) prediction model: We will develop a risk prediction model for BPD diagnosed at 36 weeks, based on a combination of proteins, imaging and clinical measures (minimum 7 inputs) derived within the first 7 days after birth. Model development will include several steps starting with methods for variable selection and model fitting to testing the performance and validation of models. To test measures originally significantly associated with BPD, and identify other measures that are predictive of BPD, binary logistic regression, multiple forward stepwise logistic regression, and other classification models will be evaluated with likely measures as covariates. This approach is similar to other recent studies that developed prognostic, biomarker-based models for predicting adverse outcomes in adults with respiratory problems. (34) Model performance and discrimination will then be evaluated. Internal validation with both cross-validation and bootstrapping methods to adjust for model over-optimism and bias towards inherent overestimated performance metrics will be applied. A similar strategy will be used for developing and testing risk prediction models at 1 and 2 years, which will include initial variable selection and subsequent model performance (AUC, discrimination) and validation (cross-validation) tests. We will examine several methods (e.g. growth curve trajectory) for coding repeatedly measured predictor variables that best capture developmental changes related to lung injury over time and subsequent respiratory risks. Cox proportional-hazards regression models and Kaplan-Meier survival curves will be used to further investigate and illustrate differences in BPD risk outcomes between high-risk and low-risk groups based on prognostic scores derived from BPD risk models, which will be useful to account for infants that may be lost to follow-up before 2 years.

Testing and developing alternative machine learning models of BPD risk.

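### The synopsis claims sufficient power for the endotyping and the 1- and 2-year objectives, but the only sample-size calculation is for the 36-week BPD model and is not a power calculation

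*Protocol*

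**What the plan says.** The synopsis, under Study Population, states: "This sample size will have sufficient power to address the endotyping and respiratory health", continuing "objectives of the study at 1- and 2-years corrected age, with account for anticipated loss to follow up rates". No significance level, power, effect size or number of classes accompanies it.

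Section 11.1 gives a narrower purpose: "The sample size for BLUEPRINT is designed to address the robustness of early respiratory phenotypes identified predicting BPD". Its inputs are a BPD prevalence ("The prevalence of survival with BPD within the ANZNN is 0.69") and the assumption that "a moderate C-index of 0.75 is achievable". From these it prints minimum sizes of 500, 550 and 600 infants for 10, 11 and 12 predictors. For follow-up it gives only a head count: "approximately 400-450 surviving infants available for 2-year follow up", assuming retention above 80% after discharge.

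Two other places show what the synopsis sentence has to cover. The primary outcome in Section 3.2, Table 3a, is "Functional endotypes defined from clinical, plasma protein and lung imaging measures using latent class analysis". Section 11.2 adds follow-up prediction models: "A similar strategy will be used for developing and testing risk prediction models at 1 and 2 years".

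**The concern.** The synopsis makes a positive claim of adequacy for the primary objective and for the follow-up objectives, and nothing in Section 11.1 was calculated for either. This is not a detail left to the statistical analysis plan. The protocol has already made the statement, and a later document cannot supply the basis for it retrospectively.

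Two things are at stake. First, if the 1- and 2-year models are taken as adequately sized, they may be built with as many terms as the BPD model on fewer children, and so be more overfitted than the standard set for BPD. Second, secondary objective 8 compares early endotypes with the BPD diagnosis as predictors of later respiratory outcome. A reader relying on the power claim could take an inconclusive comparison as evidence that endotypes add nothing.

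**Working it through.** **1. What was sized.**

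| Objective | Given in Section 11.1 | Not given |
|---|---|---|
| Endotypes by latent class analysis (primary) | nothing | number, size and separation of classes |
| BPD model at 36 weeks | prevalence 0.69, C-index 0.75, 10-12 predictors, N 500/550/600 | nothing relevant here |
| 1- and 2-year models and endotype relations | head count 400-450 | prevalence, C-index, number of predictors, effect size, alpha, power |

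**2. Reproducing the printed figures.** The C-index of 0.75 was converted to a Cox-Snell R² by simulation. The linear predictor was normal in each outcome group with SD 1 and mean difference √2 × Φ⁻¹(0.75), with 1,000,000 records at prevalence 0.69. This gives R² = 0.162. The overfitting criterion is

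N = P / [(S − 1) ln(1 − R²/S)],

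where P is the number of parameters and S the target shrinkage. The protocol does not state S; 0.90 is assumed. Then

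(0.90 − 1) × ln(1 − 0.1617/0.90) = 0.0198 per child,

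so N = 505, 556 and 606 for P = 10, 11 and 12, against the printed 500, 550 and 600. The agreement supports the assumed S. The other two criteria need fewer: for P = 10, limiting optimism in R² needs 253, and estimating overall risk to ±0.05 needs 329.

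**3. Follow-up number with the BPD inputs.** The printed figures are 50 infants per predictor (500/10 = 550/11 = 600/12). Hence 400/50 = 8 and 450/50 = 9. The simulated R² gives 400 × 0.0198 = 7.9 and 450 × 0.0198 = 8.9; the difference is simulation and rounding error. Both ends of 400-450 lie below the printed minimum of 500 for 10 predictors.

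Expected shrinkage if 10, 11 or 12 parameters were used anyway:
- 400 children: 0.877, 0.867, 0.857
- 450 children: 0.889, 0.880, 0.870

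All are below 0.90. Seven parameters need 354 children and eight need 404.

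**4. Varying what the protocol does not state.** Parameters supported at 400 / 450 children, S = 0.90, from 300,000 simulated records per cell:

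| Outcome prevalence (assumed) | C-index 0.70 | C-index 0.75 | C-index 0.80 |
|---|---|---|---|
| 0.20 | 3.8 / 4.2 | 6.0 / 6.8 | 9.1 / 10.2 |
| 0.30 | 4.9 / 5.5 | 7.8 / 8.8 | 11.6 / 13.1 |
| 0.50 | 5.8 / 6.5 | 9.2 / 10.3 | 13.7 / 15.4 |
| 0.69 | 5.0 / 5.6 | 8.0 / 9.0 | 11.9 / 13.4 |

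At C-index 0.75, 12 parameters need at least 522 children at every prevalence tried (0.10-0.69). At 0.80, 12 parameters need about 405 at prevalence 0.69 and 413 at 0.30.

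**5. Endotyping and association objectives.** No arithmetic is possible. The pmsampsize criteria control overfitting and precision of a regression model. They say nothing about recovering latent classes or detecting a difference between them.

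**The case against.** The strongest reply is that the protocol fixes no model size for follow-up. The strategy said to be similar in Section 11.2 concerns variable selection, performance and validation; the 10-12 predictors belong to the BPD model. The only other figure there, a minimum of seven inputs, also belongs to the BPD model, and seven parameters at the BPD inputs need 354 children, which 400-450 meets. With a C-index of 0.80, even 12 parameters could fit. All of this stands.

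A reader might therefore infer too much in three ways:
- That the protocol's own tool contradicts sufficiency outright. It does not, because the deciding inputs are unstated.
- That the follow-up models should be capped at a fixed seven or eight parameters. That figure depends on a borrowed C-index and prevalence, and on truncating values close to 8 and 9.
- That the endotype-versus-BPD comparison is demonstrably underpowered. Any such figure rests on a chosen effect or class size, and the protocol specifies neither.

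Nor is the head count wrong. Compounding the 5% loss, 7% mortality and 80% retention gives 550 × 0.95 × 0.93 × 0.80 = 389, but 80% is the floor. At 85-90% retention the same product is 413-437.

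Internal validation is also planned: cross-validation and bootstrapping for BPD, cross-validation for the follow-up models. This would help reveal overfitting, but it does not make the sample sufficient.

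None of this supplies a basis for the synopsis sentence. It shows that adequacy depends on inputs the protocol never states.

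**Conclusion.** The sufficient-power statement is unsupported for the endotyping and for the 1- and 2-year objectives. That conclusion needs no outside figure: the one calculation concerns another outcome and is not a power calculation.

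For the follow-up models, 400-450 children support about 8-9 parameters rather than 10-12, provided that C-index 0.75, prevalence 0.69 and shrinkage 0.90 carry over. With the C-index at 0.70 the range is about 4-6, and at 0.80 about 9-15, over prevalence 0.20-0.69. The documents do not decide between these, so the proper conclusion is that sufficiency has not been shown. The BPD calculation itself reproduces and is not in question here.

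**What to change.** - Delete the sufficient-power sentence from the synopsis or qualify it, and state there and in Section 11.1 that N was derived for the 36-week BPD model only.
- Limit the candidate parameters of the 1- and 2-year models to the number pmsampsize supports at the children actually followed and the observed outcome prevalence, with a C-index stated in advance. Count interactions and non-linear terms, as Section 11.1 already does.
- Present the endotype objectives and the endotype-versus-BPD comparison as estimates with 95% confidence intervals and no power claim, so that an inconclusive difference is not read as equivalence.

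The cost is a change of wording and a rule for model size. No extra infants or data are needed. The downside is a less favourable statement and possibly smaller follow-up models.
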